This project has received funding from the European Union's Horizon 2020 research and innovation programme under grant agreement No 681040". The information featured only reflects the author's view and that the Commission is not responsible for any use that may be made of the information it contains.

Appendix 4:

Respeck

[figure not shown]
RESpeck Device

Wireless patch with a three-axis accelerometer

Sealed case and self-adhesive pouch

Measures chest wall rotations as the wearer breathes

Provides a respiratory effort waveform, respiratory rate and patient activity data

Specknet

Wireless Healthcare of COPD

- Wireless patch worn on the torso
- Re-useable wireless sensor module
- Contained in a single-use sleeve for hygienic attachment to the torso
- Data collection and processing in a base-station via ultra low power wireless link
- Transmitted via broadband internet or via GPRS to server
- Remote respiratory monitoring service

Specknet

Respiratory Monitoring Service

- Daily reports summarising hourly trends
- Option to access historical data
- Respiratory rate, respiratory effort/flow, activity, heart rate, cough frequency, speech episodes
- Remote examination of patient's breathing in real-time

Specknet

Patient-centric design

- Long-term wear
 - Light-weight - 17gms (incl. battery)
 - Unobtrusive - 4.5 x 3.7 x 1.3 cm
 - Battery lifetime - 12 months
- Ease of use
 - No recharging of batteries
 - Data stored on wireless patch and downloaded to the base-station when within range – no manual intervention
- Remote monitoring of performance of sensor devices for scalable deployment
 - Diagnostic data on sensor performance
 - Wireless patch replaced due to malfunction or before the battery runs out

Specknet

ORIGINAL RESEARCH

Lightweight physiologic sensor performance during pre-hospital care delivered by ambulance clinicians

Alasdair J. Mort · David Fitzpatrick · Philip M. J. Wilson · Chris Mellish · Anne Schneider

Received: 16 July 2014 / Accepted: 23 February 2015 / Published online: 25 March 2015
The Author(s) 2015. This article is published with open access at Springerlink.com

amplitude and acceleration in multiple directions. For example, the patient may be moved in the process of immediate, potentially life-saving management. This might include clearing the patient's airway, inserting a device that protects the airway, conducting chest compressions where the patient is in cardiac arrest, or moving an unconscious but breathing patient into the recovery position.

Patients must also be moved to a location where they can receive definitive treatment for their illness and/or injury. However, it may take more than one journey and there may be intercurrent treatment at more than one site before definitive care is reached. In most cases pre-hospital patients are transported by emergency ambulance, which in the United Kingdom are staffed by a mixture of qualified Paramedics and

Technicians; those qualified to a lower level than Paramedics with a smaller skill-set. The time taken to transport patients to hospital can vary greatly, influenced mainly by the geographic site of the emergency. That is, it can take much longer to transport rural patients to hospital than it might do in urban centres. Much of the patient assessment and physiologic monitoring conducted by rural ambulance clinicians thus takes place during road and air transit.

Standard physiologic parameters (e.g. blood pressure, heart rate, respiratory rate) play a key role in the triage of pre-hospital patients as they may indicate present and future patient deterioration. For example, validated systems such as the National Early Warning Score are now widely used [1]. Hillman et al. [2] reported serious physiological abnormalities in 29 % of patients in the 8 h prior to death (excluding cardiac arrests and deaths whilst in intensive care). Also, one-third of patients who did not have 'do not resuscitate' orders had persistently abnormal physiology for 2 days prior to death. The physiologic abnormality reported most often was hypotension, followed by tachypnoea, then tachycardia. Other studies have also reported considerable instability in standard physiologic measures prior to a major, life-threatening event (e.g. respiratory arrest, cardiac arrest, haemorrhagic hypotension) [3–5], although this is not always the case [6, 7].

The physiologic monitoring systems operated by ambulance clinicians most often take the form of a single device that measures several parameters. For example, the Scottish Ambulance Service operated the Philips HeartStart MRx system (Philips, Netherlands), which apart from being a defibrillator measured blood pressure on the upper-arm, and blood oxygen saturation and heart rate through a pulse oximeter attached to a finger. The monitor also captured a 12-lead ECG, and could be linked via Bluetooth to a mobile phone from where the ECG was transmitted to a coronary care unit for expert advice. Monitors like these are suitable for ambulance use as they are rugged and can be removed from the vehicle to conduct monitoring where a patient is located (e.g. in their house, by the roadside). However, they tend to be relatively heavy (due to battery requirements) and the sensors are wired. Wires can be snagged, pulling on the site of attachment resulting in spurious readings and even pulling the sensor(s) off the patient altogether. There have also been anecdotal reports of emergency workers accidentally cutting cables during the extri-

cation process. Such systems provide continuous monitoring, although the recording of individual values to care provider files is usually performed manually, limiting the volume of data recorded to perhaps two or three data points (depending upon the duration of patient transport). There is evidence that having a much larger volume of physiologic data is a better predictor of later mortality than relying upon a single value [8].

Lightweight wireless physiologic monitors are now in existence, developed partly through an international effort to enable and enhance the monitoring of patients in their own homes (i.e. telehealth). We propose that such monitors could play a major role in the future of pre-hospital care, employed by ambulance clinicians where lightweight, wireless monitoring could convey an advantage over current heavy, wired systems. We also contend that these monitors may be beneficial to Community First Responders (CFRs) who volunteer to deliver basic first-aid for ambulance services whilst an emergency ambulance is on its way. Such devices, if simple to apply and use, could greatly increase the volume of data that such personnel are able to capture, and potentially alert them to patient deterioration that they may be able to address within their limited skill-set. Facilitating the capture of more physiologic data is particularly important given the general lack of evidence to support CFR activity; this would help to inform their practice and policy. However, this is only applicable if such technology can deliver accurate data reliably during the unstable and unpredictable context of pre-hospital care.

Commonly-recorded physiologic parameters are influenced by motion and in turn display artefact or ‘noise’; physiologic waveforms deviate from their ‘normal’, characteristic patterns and erroneous data are potentially reported to the user. Such error could take the form of falsely low or high readings, often triggering alarms that then distract the operator from keeping a physical watch on the patient. Most physiologic sensors include some form of signal processing so that they can continue to deliver data in the face of motion or extreme physiologic compromise. However, it is reasonable to postulate that there is a threshold beyond which a physiologic sensor will no longer be able to deliver accurate data; for example, if finger perfusion is so low that it is impossible to generate valid blood oxygen saturation and pulse data.

The aim of our study was to explore the impact of ambulance clinician patient management and transport on defined parameters recorded from patients by two lightweight physiologic sensors. This contributed to the University of Aberdeen Managing Information in Medical Emergencies (MIME) project (see www.dotrural.ac.uk/mime), which developed and evaluated technology to support CFRs at the scene of rural medical emergencies [9].

2 Materials and methods

2.1 Design

The study employed a ‘field-function’ design, which involved controlled ‘pseudo-deployment’ of the physiologic sensors in a real-life situation [10].

2.2 Setting

The study took place at a Scottish Ambulance Service station in the north of Scotland, UK (Fig. 1). The station responded to a variety of types of call-outs originating from urban and rural areas.

2.3 Participant identification and recruitment

2.3.1 Ambulance clinicians

Clinicians from two station ‘watches’ were invited to take part. Clinicians attended an evening presentation at which the study and their proposed role in the research were described. All clinicians who volunteered to take part were asked to provide written, informed consent.

2.3.2 Pre-hospital patients

The first approach to patients was made by recruited ambulance clinicians according to set inclusion criteria (Table 1). The decision of whether or not to approach each patient was made ultimately at clinicians’ discretion. They were only to approach patients if the application of the physiologic sensors did not interfere with the timely delivery of their ‘usual’ care.

The first stage of consent involved clinicians describing the study to patients verbally. Patients were given the opportunity to ask any questions, and if they were happy to proceed they provided verbal informed consent on-scene. A preliminary verbal informed consent was deemed appropriate considering the relatively low risk nature of the study. The second stage of consent involved sending patients an opt-out form to their home address within a study information pack, at least 2 weeks after their contact with

Fig. 1 Scottish Ambulance Service emergency vehicle

the research. Whilst consent mechanisms based on opting out are not the norm, these have previously been carried out in other pre-hospital emergency care research where patients were in a vulnerable state immediately after their emergency care visit, and are well recognised as being a difficult group to make contact with [11, 12]. We considered opt-out consent to be satisfactory in this situation where there was no significant risk of harm to participants and no risk to patient confidentiality. An opt-in approach could have resulted in lower recruitment and therefore lower generalisability of the results [13].

The local NHS Health Board was contacted prior to mailing study information packs in order to establish whether or not patients had been discharged from hospital. Patients who had died and those who completed the opt-out form were excluded from the study. All patients who participated were given a unique identification number in order to anonymise their involvement.

2.4 Physiologic parameters

Three physiologic parameters were selected to monitor; respiratory rate (RR), heart rate (HR) and blood oxygen saturation (SpO₂). RR was chosen as it is an essential clinical parameter that traditionally is difficult to monitor both reliably and repeatedly in anything but a resting, motionless patient. Indeed, RR has previously been described as the 'neglected vital sign' [14]. In the pre-hospital environment, ambulance clinicians will monitor RR by counting the rise and fall of the patient's chest/abdomen and/or the misting and de-misting of a non-rebreathing oxygen mask (not including RR monitored using capnography in the intubated patient). This means that only a small number of RR data points are recorded during the time that ambulance clinicians are with the patient. HR and SpO₂ were selected as they are also parameters that are monitored ubiquitously in the pre-hospital environment using pulse oximetry.

Respiratory rate, HR and SpO₂ formed the basis of a novel pre-hospital physiologic monitoring system that we developed within our research group for use by Ambulance Service CFRs. They are all parameters that can be monitored using lightweight physiologic sensors that are simple and quick to apply by non-medical experts.

2.5 Physiologic sensors

Two lightweight, non-invasive physiologic sensors were selected for application to ambulance patients. The first was the Contec Medical Systems CMS50FW pulse oximeter (Contec Medical Systems, Qinhuangdao, China), which monitored SpO₂, HR and also displayed the photoplethysmograph to the user.

Table 1 Pre-hospital patient inclusion and exclusion criteria

Inclusion criteria	Exclusion criteria
Adults (18 years and above)	Unable to understand verbal explanations given in English—also including those with special communication needs
Males and females	Patients with injuries or in a position that prevented application of the sensors
Ability to represent own interests and to provide verbal, informed consent	
Able to apply the sensors to the patient	

The CMS50FW had Bluetooth capability to send data wirelessly. However, this facility was turned off in this study and the data stored on the device instead (NOT including photoplethysmograph data). Capturing data wirelessly would have necessitated a separate laptop computer and time-consuming device pairing, both of which were inappropriate in the space-restricted and time-dependent emergency ambulance environment. Non-averaged HR and SpO₂ data were recorded in a comma separated value file at a rate of 1 Hz.

The second monitor was the RESpeck RR sensor (University of Edinburgh Department of Speckled Computing, School of Informatics, Scotland), which was an encapsulated tri-axial accelerometer positioned on the left side of the abdomen just under the costal margin. RESpeck recorded changes in abdominal position in three orthogonal axes, relative to gravity. These data were automatically integrated and differentiated into a derived ‘activity’ signal, and a RR signal with a shape similar to inspiratory and expiratory flow. RESpeck had been verified to be a reliable measure of RR when compared with RR derived from a nasal cannula in anaesthetised post-operative patients; instantaneous RESpeck RR matched the routine clinical measurement of RR within two breaths per minute (bpm)—an acceptable limit of accuracy employed previously—on 86 % of occasions, with a mean absolute difference of 0.6 bpm [15]. However, our study was the first time that RESpeck had been implemented in the pre-hospital environment. RESpeck was entirely wireless and all data were transmitted using a Bluetooth 4.0 Low-Energy protocol to an iPod (Apple, Cupertino, CA, USA) on which the data were displayed and recorded. Accelerometer data were recorded at a rate of 12.5 Hz. Figure 2 displays both

medical sensors and their method of attachment to the body.

2.7 Data analysis

2.7.1 Pulse oximetry

Heart rate and SpO₂ data were initially reviewed and plotted to explore for any gross deviations from ‘normal’ physiologic values. In particular, the pulse oximeter logged a non-physiologic value of 255 BPM for HR and 127 % for SpO₂ when the sensor was removed from the finger, or if finger attachment was sub-optimal. The frequency of such values was noted. The maximum, minimum, mean and standard deviation for HR and SpO₂ were then calculated on a patient-by-patient basis. Further analyses explored for the presence and length of any periods of pulse oximeter data that appeared ‘abnormal’. Our definition of ‘abnormal’ also included any incidence of a sudden, apparently non-physiologic, increase or decrease in blood oxygen saturation and/or heart rate from a stable value. The total time that each sensor exhibited ‘abnormality’ was expressed as a percentage of the total monitoring time. This was also expressed as the proportion of

‘abnormality’ at nominal rest, and the proportion of ‘abnormality’ during ambulance transit, in order to explore for any apparent impact of gross motion on signal quality.

2.7.2 Respiratory rate

RESpeck files were downloaded from the iPod and the gross activity and breathing signals were plotted. Patient management data were plotted on top of each trace, noting

in particular the start and end of gross motion associated with ambulance transit. The raw data files were then processed post hoc using proprietary software (University of Edinburgh), which produced a separate file containing time and validated RR data. The software actively excluded any data captured in excess of a pre-defined movement threshold. This meant that only the fine movements associated with breathing were analysed, and that larger movements not associated with breathing were omitted. The number of validated breaths captured before, during and after ambulance transit were noted. The maximum, minimum and mean number of validated breaths captured before and after ambulance transit per minute was also calculated; zero data (i.e. where no validated breaths were produced per minute) were included in the mean data. Finally, maximum, minimum, and the mean (± 1 SD) RR were recorded.

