RESpeck is a monitoring device, which collects data via low power wireless link for processing at base-station in patient's home. RESpeck had been verified to be a reliable measure of RR when compared with RR derived from a nasal cannula in anaesthetised post-operative patients; instantaneous RESpeck RR matched the routine clinical measurement of RR within two breaths per minute (bpm) an acceptable limit of accuracy employed previously—on 86 % of occasions, with a mean absolute difference of 0.6 bpm. (15. Drummond GB, Bates A, Mann J, Arvind DK. Validation of a new non-invasive automatic monitor of respiratory rate for post-operative subjects (Br J Anaesth. 2011;107:462–469. doi: 10.1093/bja/aer153). It will be transmitted to a server at the Centre for Speckled Computing via broadband internet where the data will be analysed. RESpeck files will be downloaded from the iPod or Android tablet and the gross activity and breathing signals will be plotted. The raw data files will then be processed post hoc using proprietary software (University of Edinburgh), which produces a separate file containing time and validated RR data. The software will actively exclude any data captured in excess of a pre-defined movement threshold. This means that only the fine movements associated with breathing will be analysed, and that larger movements not associated with breathing will be omitted. The number of validated breaths captured before, during and after exposure to SHS will be noted. The maximum, minimum and mean number of validated breaths captured before and after SHS exposure per minute will also be calculated; zero data (i.e. where no validated breaths are produced per minute) will be included in the mean data. Finally, maximum, minimum, and the mean (± 1 SD) RR will be recorded. (Appendix 4),

AIRSpeck:

AIRSpeck Personal/mobile monitor will be used for exposure measurements (Appendix 5)

- Includes humidity sensor and improved WiFi range
- Detect indoor fine particulate matter (dust, smoke, exhaust, etc.)
- Plot trends over time with our free visualization tools
- Access your home's data from your smart phone or computer anywhere, anytime
- Compare indoor and outdoor* air quality readings on screen

Patient Schedule:

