3.4 Respiratory rate

The RESpeck sensor was applied successfully to 14/16 patients. On two occasions the patient's clothing impeded

application to the abdomen. On average, 40 % of activity data were below the pre-defined activity threshold, and 60 % (± 18.9 , 1 SD) were above it. This meant that 60 % of data were actively excluded from the RESpeck post hoc analysis. However, the proportion of data in excess of the activity threshold ranged between 27.4 and 86.5 % in individual patients, meaning that the level of motion varied widely.

The total number of validated breaths captured at nominal rest (i.e., without the gross motion associated with ambulance transit) during individual patient management ranged from 5 to 255, with an average of 54.6 breaths captured per patient (± 65 , 1 SD). The maximum number of validated breaths returned by RESpeck for each patient ranged between 3 and 18 breaths per minute. The mean number of validated breaths reported per minute, including zero values for minutes where no validated breaths were returned, ranged from 0.5 to 7.9 (overall mean across all patient data = 4.2 ± 2.2 , 1 SD). Breathing rate ranged from 5.3 to 35.3 breaths per minute, whilst mean breathing rate for each patient ranged from 9.7 to 21.2 breaths per minute.

Only 29 validated breaths were captured during ambulance transit across 3/11 patients (n = 15, 12, 2), compared to 765 breaths recorded at nominal rest from 14 patients.

4 Discussion

This was the first study of its kind to robustly measure the impact of pre-hospital motion on commonly monitored physiologic parameters. Our research study identified some form of error in nearly every blood oxygen saturation, heart rate and breathing rate signal. For most pre-hospital patients error accounted for a relatively small proportion of

pulse oximeter recording. The breathing rate sensor delivered considerably less data, but still produced many more data points than would be achievable through manual assessment alone.

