This was the first application of the RESpeck breathing rate sensor in a pre-hospital context. However, no validated breathing rates were delivered by the sensor during ambulance transit; the fine excursions of the abdomen with breathing were lost amongst the large, random movements of the ambulance. Also, even the entry and exit of clinicians into and from the ambulance (without the patient) was sufficient for it not to deliver validated data. Despite this, only reporting on rhythmic, regular breaths is more diagnostic than reporting on irregular, noisy breathing rate data. For example, Chen et al. [23] employed the technique of impedance pneumography (measuring the changes in resistance across the chest with breathing, using a conventional electrocardiogram trace) combined with a novel algorithm (applied retrospectively) on 898 trauma patients monitored during helicopter transit. Breathing rate based upon reliable breaths only was a better predictor of a patient receiving a respiratory intervention at a later stage, and of identifying patients with haemorrhage. Impedance pneumography (available on some pre-hospital multi-parameter monitoring systems) will inevitably capture more data on respiratory rate than the RESpeck during gross motion. However, our proposed model of employing the RESpeck on pre-hospital patients managed by Community

First Responders will not mean exposure to ambulance transit. As such, the RESpeck may be an effective way for non-experts to gather considerably more breathing rate data than would be achievable using manual methods alone. It may also be more objective.

There were some limitations to this study. Pulse oximeter photoplethysmograph data were displayed on the

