In contrast, the design of AirSpeck-P as a body-worn personal exposure monitor gives prominence to size, weight and wearability issues and an App running on the mobile device orchestrates its operation to measure particulate matter and two gases (NO_2 and O_3).

Fig 1. (Top-left) AirSpeck-S monitor attached to a lamp post in the Meadows area in Edinburgh (Top-right); (Bottom-left) AirSpeck-P monitor worn as a belt (Bottom-right).

high intensity laser source to illuminate the particle as it passes through the detection chamber and the redirected light is detected by a photo detector. It also outputs derived concentrations in PM1, PM2.5, and PM10 equivalent ratios. The 5V rail supplying the OPC and other external sensors are switched off between measurement sessions to extend the battery lifetime.

[figure not shown]

Fig 2. Block diagram of the principal components of the AirSpeck hardware platform.

A. Sensors

Optical Particle Counter (OPC): The OPC is connected to the AirSpeck using an SPI interface and powered from the 5V rail along with the other external sensors. It provides particle counts in 16 bins categorised in terms of ranges of spherical equivalent sizes between $0.38\mu\text{m}$ to $17\mu\text{m}$ (Figure 3). It uses a

Fig. 3. A “spectrum” of particulate numbers (Y-axis) over time (X-axis) ranging in diameter sizes between $0.38\mu\text{m}$ and $17.0\mu\text{m}$ distributed across 16 bins (inset) detected by the laser-based Optical Particle Counter (OPC).

Temperature & Humidity Sensors: A Sensirion SHT21 temperature and humidity sensor [6] is included on the AirSpeck PCB to enable integrated sensing of temperature and humidity without requiring the connection of external sensors.

FS200 Temperature & Humidity Sensor: An interface is provided for the FS200 waterproof temperature and humidity sensor, comprising a Sensirion SHTXX series temperature and humidity sensor [7] in a waterproof (sintered metal) enclosure. This sensor is placed to protrude outside the enclosure either into the ambient air or into the soil for measuring soil moisture content.

B. Processing and Communication

Bluetooth Low Energy (BLE): The NRF51822 SoC [8] has an in-built Bluetooth LE radio which communicates with a custom Android Application on the mobile device for receiving and stamping the sensor data with time and location (GPS) information and then forwarding them to the server via the cellular network or WiFi.

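### The adapted RESpeck method no longer marks vehicle motion, so any journey enters the before and after summaries as activity and as zeros in the validated-breath count

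*Combined protocol and SAP*

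**What the plan says.** The protocol's RESpeck section (under the devices used to gather data) follows section 2.7.2 of the paper in Appendix 4 almost sentence for sentence.

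- **Periods compared.** Source: "The number of validated breaths captured before, during and after ambulance transit were noted". Protocol: "The number of validated breaths captured before, during and after exposure to SHS will be noted".
- **Marking the trace.** After plotting the signals, the source overlaid patient-management data, noting "in particular the start and end of gross motion associated with ambulance transit". The protocol goes straight from plotting to processing: "the gross activity and breathing signals will be plotted. The raw data files will then be processed post hoc using proprietary software". The overlay step is gone.
- **Zero rule.** Both texts count minutes with no validated breath as zero in the mean number of validated breaths per minute.
- **Respiratory rate.** Both texts exclude data above the movement threshold before breaths are validated, and summarise respiratory rate as a separate, final item.

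The Primary Endpoints section names changes in respiratory rate, flow and activity levels. The Patient Schedule puts the fitting visit at least 2 to 4 hours before exposure and the return visit at least 24 hours after. Appendix 6 records the start and end of exposure and has a free-text line for unusual events, but no travel times.

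**The concern.** Appendix 4 shows that the sensor responds to the vehicle as well as to the wearer. On yield it reports: "Only 29 validated breaths were captured during ambulance transit across 3/11 patients (n = 15, 12, 2), compared to 765 breaths recorded at nominal rest". Its discussion adds that "even the entry and exit of clinicians into and from the ambulance (without the patient) was sufficient for it not to deliver validated data". The activity signal comes from the same accelerometer (Appendix 4, section 2.5), and no correction for vehicle motion is described. A participant sitting still in a car or bus could therefore be logged as active while yielding few or no validated breaths.

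Participants are fitted at a centre, go to a venue and later return, so travel falls in both the before and after periods. If those periods differ in length, the same journey takes up a different share of each. The two summaries then shift in opposite directions for reasons unrelated to smoke, by an amount that depends on how far and by what means each person travelled.

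**Working it through.** **Source figures (Appendix 4, section 3.4).** Breaths in transit: 15 + 12 + 2 = 29, as stated. Breaths at rest per patient: 765 / 14 = 54.64, against 54.6 stated. Transit therefore gave 29 / (29 + 765) = 3.7% of validated breaths, or 29 / 11 = 2.6 per transported patient, not adjusted for time. Treating travel minutes as zero is close to these data.

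**Inputs from the documents.** Mean validated breaths per minute, zeros included: 4.2, SD 2.2 (Appendix 4, section 3.4). Patients per disease group: 30. Significance level: 0.05 with a Student t test; sidedness is not stated, and two-sided is used here.

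**Assumptions.** Vehicle travel of 15 or 30 minutes in each period; a before window of 2 or 4 hours and an after window of 24 hours, taken from the minimum visit spacing because no analysis windows are defined; no validated breaths in travel; 4.2 per minute otherwise; a paired-difference SD of 2.2, borrowed from the source's spread around its overall mean; no true effect of smoke.

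**Formula.** Mean count = 4.2 × (1 − travel minutes / window minutes). The chance of p < 0.05 comes from the noncentral t distribution with 29 degrees of freedom and noncentrality (difference / 2.2) × √30.

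| Travel per period | Before window | Before mean | After mean (24 h) | False rise | Chance of p < 0.05 |
|---|---|---|---|---|---|
| 15 min | 2 h | 3.68 | 4.16 | 0.48 | 21% |
| 15 min | 4 h | 3.94 | 4.16 | 0.22 | 8% |
| 30 min | 2 h | 3.15 | 4.11 | 0.96 | 64% |
| 30 min | 4 h | 3.68 | 4.11 | 0.44 | 18% |
| 30 min | 8 h | 3.94 | 4.11 | 0.18 | 7% |

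**Sensitivity.**
- With equal windows and equal travel (30 of 120 minutes on both sides), both means are 3.15. The difference is zero and the error rate is the nominal 5%, although both values are too low.
- If the after period also includes a 30-minute trip back to the centre, its mean is 4.2 × (1 − 60/1440) = 4.03. The false rise becomes 0.35 to 0.88, and the chance of p < 0.05 becomes 13% to 56%.
- At 30 minutes of travel and a 2 to 4 hour before window, an SD of 3.0 gives 12% to 40% and an SD of 1.5 gives 34% to 92%.

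**Activity.** Thirty minutes is 30/240 = 12.5% to 30/120 = 25% of the before window, and 30/1440 = 2% of the after window. Activity would appear to fall after exposure while the validated-breath count appears to rise.

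**Respiratory rate.** Above-threshold data are removed before the rate is derived, so travel minutes add no zeros to it. The rate rests on fewer minutes, but this mechanism does not lower its mean.

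**The case against.** The best defence is that transit was the source study's own research question. It was marked because it was the event of interest, and substituting smoke exposure is ordinary adaptation. That is fair as to intent. It does not change the result: the adapted text has no means of recognising vehicle motion, which becomes a nuisance factor in the new setting.

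Four further points stand and limit the finding.

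- A reader might infer that respiratory rate itself is biased, or that the sensor records absence of breathing. The documents do not support this. Above the threshold the sensor delivers no rate, and the zero rule applies only to the validated-breath count, which measures data yield and is not named among the primary endpoints.
- A reader might infer that the source reported breathing at rest only. It reported rest separately ("The total number of validated breaths captured at nominal rest (i.e., without the gross motion associated with ambulance transit") and also gave the 29 breaths in transit. Its abstract and discussion say that transit gave no validated breaths, which conflicts with its own results.
- Mode and length of travel are nowhere stated, participants are fully ambulatory, and walking would be genuine activity. The motion evidence comes from emergency ambulances; cars or buses may differ.
- The visit spacings are minimum intervals, not analysis windows, and the size of the effect depends heavily on the windows.

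**Conclusion.** The point holds in a limited form. As written, any vehicle journey enters the before and after summaries of activity, part of a primary endpoint, and of the validated-breath count, and no rule prevents it. Mean respiratory rate loses data but is not pulled toward zero.

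The size cannot be fixed from the documents. Under the stated assumptions the false rise in validated breaths is about 0.2 to 1.0 per minute, with 8% to 64% false positives. It shrinks as the windows become more alike and vanishes when windows and travel are equal. It would be tempting to read the 64% as the error rate of the primary analysis. It is not: it concerns the yield count and needs the shortest before window, the longer travel time and the borrowed SD together. The effect on activity is an inference from the shared accelerometer; the documents give no activity data from which to size it beyond the share of each window spent travelling.

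This should be corrected before data collection, because travel times that are not recorded at the time may be unrecoverable.

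**What to change.** In the RESpeck section:

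1. Define the before and after windows.
2. Exclude vehicle-travel minutes from the activity and validated-breath summaries, or report them separately.
3. Report valid minutes per period beside respiratory rate.

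In Appendix 6, add start and end times for each vehicle journey and use these as the main source. The app described in the Appendix 5 paper works by "receiving and stamping the sensor data with time and location (GPS) information", and that paper plots a speed trace that shows car journeys. The protocol does not say that this log will be kept. Use it only if it is in fact recorded, its clock can be aligned with the RESpeck, and its use fits the de-identification rule under Data Management, since a location trace can reveal a home address.

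The cost is a few sentences, two time entries per journey and a short filtering step. The downside is that some minutes are dropped, few of which would have yielded validated breaths, and that the exclusion depends on times recorded by patients.
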